5.2.3 Assessment of safety laboratory parameters

The laboratory tests will be performed as listed in [Table 5.2.3: 1](#) and [Table 5.2.3: 2](#). Instructions on sample collection, sample handling/ processing, and sample shipping will be provided to the investigator site file by the central laboratory. For time points of laboratory sampling, see [Flow chart 1](#), [Flow chart 2](#) and [Flow chart 3](#).

Laboratory results of the patients will be available in real time to the respective investigator and to the clinical monitor of each country (central laboratory website), and selected abnormal laboratory alerts will be sent automatically to the sites and to the sponsor in real time. PK, PD and biomarker data will not be available to the investigators or local clinical monitors but the Trial Team (sponsor) in a blinded manner and when relevant, in an unblinded manner to the DMC. Laboratory results will be reported as the absolute value of the measurement obtained on a study patient.

Clinically relevant laboratory values will be commented on in the eCRF. A clinically relevant value may be either in- or outside the reference range. Clinically relevant abnormal laboratory test results must be repeated using an unscheduled visit lab kit and must be repeated until normalisation or stabilisation or until an alternative explanation has been found. Clinically relevant abnormal laboratory values will be also graded for intensity by using RCTC Version 2.0 criteria.

Table 5.2.3: 1 Laboratory tests

Category	Test name
Hæmatology	Hematocrit (Hct) Hemoglobin (Hb) Red Blood Cell Count / Erythrocytes Reticulocyte Count White Blood Cells / Leucocytes Platelet Count
Differential automatic (relative and absolute count)	Neutrophils Eosinophils Basophils Monocytes Lymphocytes
Differential manual (relative and absolute count) (if differential automatic is abnormal)	Neutrophils, Bands Neutrophils, Polymorphonuclear (PMN) Eosinophils Basophils Monocytes Lymphocytes
Coagulation	Partial Thromboplastin Time (PTT) Prothrombin Time (Quick / INR) Fibrinogen
Enzymes	AST/GOT, SGOT ALT/GPT, SGPT Alkaline Phosphatase (AP/ALP) Creatine Kinase (CK) CK-MB if CK is elevated Gamma-Glutamyl Transferase (GGT/γ-GT) Lactic Dehydrogenase (LDH) Lipase Amylase
Specific gamma-globulin quantification	IgE [†] , IgG

only in case of allergic reaction

Table 5.2.3: 1 Laboratory tests (con't)

Category	Test name

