7.3.3 Safety analyses

Since the main objective of this study is long term safety, the primary focus would be on incidence of drug-related AE and serious infection.

Adverse events will be coded using the Medical Dictionary for Regulatory Activities (MedDRA) coding dictionary. Summary tables and listings will be produced. All adverse events with an onset between start of treatment and end of the residual effect period (REP), a period of 20 weeks after the last dose of trial medication, will be assigned to the treatment period for evaluation.

All treated patients will be included in the safety analysis.

Statistical analysis and reporting of adverse events will concentrate on treatment-emergent adverse events. To this end, all adverse events occurring between start of treatment and end of the residual effect period will be considered 'treatment-emergent'. Adverse events that start before first drug intake and deteriorate under treatment will also be considered as 'treatment-emergent'. Frequency, severity, and causal relationship of adverse events will be tabulated by system organ class and preferred term after coding according to the current version of the Medical Dictionary for Drug Regulatory Activities (MedDRA). Safety analyses will focus on adverse events related to early discontinuation, immune suppression and injection site effects.

Laboratory data will be analysed both quantitatively as well as qualitatively. The latter will be done via comparison of laboratory data to their reference ranges. Values outside the reference range as well as values defined as clinically relevant will be highlighted in the listings. Treatment groups will be compared descriptively with regard to distribution parameters as well as with regard to frequency and percentage of patients with abnormal values or clinically relevant abnormal values. Analysis of laboratory measures will focus on haemotologic measures of immune suppression.

Vital signs, physical examinations, or other safety-relevant data observed at screening, baseline, during the course of the trial and at the end-of-trial evaluation will be assessed with regard to possible changes compared to findings before start of treatment.

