J2. Cough	Transient, intermittent, occasional OTC meds relieve	Persistent, requires narcotic or other prescription meds for relief	Recurrent, persistent coughing spasms without consistent relief by meds, interferes with function	Interferes with oxygenation; debilitating
J3. Dyspnea	Subjective, transient, no interference with function	Symptomatic, intermittent or recurring, interferes with exertional activities	Symptomatic during daily routine activities, interferes with function, treatment with intermittent nasal O ₂ relieves	Symptomatic at rest, debilitating, requires constant nasal O ₂
J4. Pleuritic pain (pleurisy)	Transient, intermittent symptoms, no treatment or OTC meds relieve	Persistent symptoms, requires prescription meds for relief	Prolonged symptoms, interferes with function, requires frequent narcotic pain relief	Debilitating, requiring hospitalisation

10.3 SEVERITY OF AE AS DESCRIBED IN THE RHEUMATOLOGY COMMON TOXICITY CRITERIA (OMERACT) (CON'T)

		1 - Mild	2 - Moderate	3 - Severe	4 - Includes Life Threatening
J. PULMONARY					
J5. Pneumonitis (pulmonary infiltrates)	Asymptomatic radiographic changes, transient, no treatment required	Symptomatic, persistent, requiring corticosteroids	Symptomatic, requiring treatment including O ₂	Symptomatic, requiring assisted ventilation	Debilitating, not reversible; or requiring assisted ventilation
J6. Pulmonary function decreased (FVC or carbon monoxide diffusion capacity— DLCO)	76–90% of pre-treatment value	51–75% of pre-treatment value	26–50% of pre-treatment value	≤ 25% of pre-treatment value	≤ 25% of pre-treatment value
LABORATORY DATA					
K. HEMATOLOGY					
K1. Hgb (g/dl) decrease from pre-treatment	1.0–1.4	1.5–2.0	2.1–2.9; or Hgb < 8.0, > 7.0	≥ 3.0; or Hgb < 7.0	≥ 3.0; or Hgb < 7.0
K2. Leukopenia (total WBC) x 1000	3.0–3.9	2.0–2.9	1.0–1.9	< 1.0	< 1.0

10.3 SEVERITY OF AE AS DESCRIBED IN THE RHEUMATOLOGY COMMON TOXICITY CRITERIA (OMERACT) (CONT)

	1 - Mild	2 - Moderate	3 - Severe	4 - Includes Life Threatening
LABORATORY DATA				
K. HEMATOLOGY				
K3. Neutropenia (x 1000)	1.5–1.9	1.0–1.4	0.5–0.9	< 0.5
K4. Lymphopenia (x 1000)	1.5–1.9	1.0–1.4	0.5–0.9	< 0.5
K5. Platelets (x 1000)	75–LLN	50–74.9	20–49.9; platelet transfusion required	< 20; recurrent platelet transfusions
L. CHEMISTRY				
L1. Hypercalcemia (mg/dl)	1.1 x ULN–11.5	11.6–12.5	12.6–13.5; or symptoms present	> 13.5; or associated coma
L2. Hyperglycemia (mg/dl) Fasting	140–160	161–250	251–500	> 500, or associated with ketoacidosis

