10.3 SEVERITY OF AE AS DESCRIBED IN THE RHEUMATOLOGY COMMON TOXICITY CRITERIA (OMERACT) (CONT)

	1 - Mild	2 - Moderate	3 - Severe	4 - Includes Life Threatening
LABORATORY DATA				
L. CHEMISTRY				
L3. Hyperkalemia (mg/dl)	5.5–5.9	6.0–6.4	6.5–7.0 or any ECG change	>7.0 or any arrhythmia
L4. Hypocalcaemia (mg/dl)	0.9 x LLN–7.8	7.7–7.0	6.9–6.5; or associated with symptoms	<6.5, or occurrence of tetany
L5. Hypoglycemia (mg/dl)	55–64 (no symptoms)	40–54 (or symptoms present)	30–39 (symptoms impair function)	<30, or coma
L6. Hyponatremia (mg/dl)	NA	125–129	120–124	<120
L7. Hypokalemia (mg/dl)	NA	3.0–3.4	2.5–2.9	<2.5

10.3 SEVERITY OF AE AS DESCRIBED IN THE RHEUMATOLOGY COMMON TOXICITY CRITERIA (OMERACT) (CONT)

	1 - Mild	2 - Moderate	3 - Severe	4 - Includes Life-Threatening
LABORATORY DATA				
L. CHEMISTRY				
L8. CPK (also if polymyositis-disease)	1.2–1.9 x ULN	2.0–4.0 x ULN	> 4.0 x ULN with weakness but without life-threatening signs or symptoms	> 4.0 x ULN with signs or symptoms of rhabdomyolysis or life-threatening
L9. Serum uric acid	1.2–1.6 x ULN	1.7–2.9 x ULN	3.0–5.0 x ULN or gout	NA
L10. Creatinine (mg/dl)	1.1–1.3 x ULN	1.3–1.8 x ULN	1.9–3.0 x ULN	> 3.0 x ULN
L11. SGOT (AST)	1.2–1.5 x ULN	1.6–3.0 x ULN	3.1–8.0 x ULN	> 8.0 x ULN
L12. SGPT (ALT)	1.2–1.5 x ULN	1.6–3.0 x ULN	3.0–8.0 x ULN	> 8.0 x ULN
L13. Alkaline phosphatase	1.1–2.0 x ULN	1.6–3.0 x ULN	3.0–5.0 x ULN	> 5.0 x ULN

10.3 SEVERITY OF AE AS DESCRIBED IN THE RHEUMATOLOGY COMMON TOXICITY CRITERIA (OMERACT) (CONT)

	1 - Mild	2 - Moderate	3 - Severe	4 - Includes Life Threatening
LABORATORY DATA				
L. CHEMISTRY				
L14. T. bilirubin	1.1–1.4 x ULN	1.5–1.9 x ULN	2.0–3.0 x ULN	> 3.0 x ULN
L15. LDH	1.3–2.4 x ULN	2.5–5.0 x ULN	5.1–10 x ULN	> 10 x ULN
M. URINALYSIS				
M1. Hematuria	Micro only	Gross, no clots	Clots, transfusion < 2 units	Transfusions required
M2. Proteinuria (per 24 h)	300–500 g (tr/1+)	501–1999 g (2+)	2–5.0 g (3+) nephrotic syndrome	> 5.0 g (4+) anasarca
M3. WBC in urine	NA	NA	Indicating acute interstitial nephritis	Associated with acute renal failure

10.3 SEVERITY OF AE AS DESCRIBED IN THE RHEUMATOLOGY COMMON TOXICITY CRITERIA (OMERACT) (CON'T)

	1 - Mild	2 - Moderate	3 - Severe	4 - Includes Life Threatening
LABORATORY DATA				
M. URINALYSIS				
M4. Uric acid crystals	Present without symptoms	NA	With stones or symptoms of stones (e.g., renal colic)	Causing renal outflow obstruction and hospitalization

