10.3.2 Statistical Methods

Changes from baseline in continuous laboratory parameters will be summarized by n, mean, standard deviation, minimum value, median, and maximum value for each treatment group.

Shift tables from baseline to the final value (the last assessment during each treatment period) according to the normal range will be provided for each hematology, clinical chemistry parameter and urinalysis parameter. The laboratory data will be categorized as low, normal, or high based on the normal ranges of the central laboratory used in this study. The shift tables will tabulate the number and percentage of subjects with baseline values below/within/above the normal range versus final values below/within/above the normal range.

For selected laboratory parameter with Common Toxicity Criteria (CTC) a listing of all subjects with any laboratory determinations meeting CTC Grade ≥ 3 as well as being a higher grade than the baseline CTC grade will be provided. For each of these subjects, the whole course of the parameter of the current study along with the baseline value will be listed.

Pre-defined criteria of CTC Grade 3 or greater are given in [Table 8](#) and [Table 9](#) below for selected chemistry variables and hematology variables respectively based on CTC Version 4.0. Please refer to Appendix [12.8](#) for the CTC Grades 1 - 4 for these variables based on CTC Version 4.0.

Table 8. Criteria for CTC Grade 3 or Greater for Chemistry Values

Chemistry Variables	Units	Definition of CTC Grade 3 or Greater	
		Very Low	Very High
TBL	mcmol/L		> 3.0 × ULN
SGOT/AST	U/L		> 5.0 × ULN
SGPT/ALT	U/L		> 5.0 × ULN
Albumin	g/L	< 20	
Glucose	mmol/L	< 2.2	> 13.9
Triglycerides	mmol/L		> 5.7
Creatinine	mcmol/L		> 3.0 × ULN
Sodium	mmol/L	< 130	> 155
Potassium	mmol/L	< 3.0	> 6.0
Calcium	mmol/L	< 1.75	> 3.1
CPK	U/L		> 5.0 × ULN
Total Cholesterol	mmol/L		> 10.34
GGT			> 5.0 × ULN
ALP			> 5.0 × ULN

Table 9. Criteria for CTC Grade 3 or Greater for Hematology Values

Hematology Variables	Units	Definition of CTC Grade 3 or Greater	
		Very Low	Very High
Hemoglobin	g/L	< 80.0	
Platelets count	10 ⁹ /L	< 50.0	
WBC count	10 ⁹ /L	< 2.0	
Neutrophils	10 ⁹ /L	< 1.0	
Lymphocytes	10 ⁹ /L	< 0.5	

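### SAP 10.3.2 grades laboratory values by CTC v4.0, not the protocol's RCTC v2.0, so RCTC Grade 3 lymphopenia and creatinine and many RCTC Grade 3–4 haemoglobin falls meet no SAP laboratory threshold

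*SAP*

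**What the plan says.** Protocol 5.2.3 sets the scale for laboratory intensity: "Clinically relevant abnormal laboratory values will be also graded for intensity by using RCTC Version 2.0 criteria". The RCTC table is in protocol Appendix 10.3. Protocol 7.3.3 states the emphasis of the laboratory analysis: "Analysis of laboratory measures will focus on haemotologic measures of immune suppression".

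SAP 10.2.1.3 keeps RCTC for adverse-event severity. SAP 10.3.2 plans a listing of subjects with any determination "meeting CTC Grade ≥ 3 as well as being a higher grade than the baseline CTC grade will be provided". The cut-offs in Tables 8 and 9 are given "for selected chemistry variables and hematology variables respectively based on CTC Version 4.0", with the full grades in Appendix 12.8.

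Two pairs of lines show the difference:

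- **Lymphocytes.** Protocol Appendix 10.3, Grades 1 to 4: "K4. Lymphopenia (x 1000) 1.5–1.9 1.0–1.4 0.5–0.9 < 0.5". SAP Table 9, Grade 3 or greater: "Lymphocytes 10 ⁹ /L < 0.5".
- **Creatinine.** Protocol Appendix 10.3, Grades 1 to 4: "L10. Creatinine (mg/dl) 1.1–1.3 x ULN 1.3–1.8 x ULN 1.9–3.0 x ULN > 3.0 x ULN". SAP Table 8 lists only values above 3.0 x ULN.

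SAP section 11 says that the sponsor's own conventions have been adopted. It does not mention the laboratory grading scale.

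**The concern.** Safety is the primary objective. In a single-group study with no hypothesis test, the threshold outputs are how a reader finds the individual subjects with marked abnormalities. If the protocol's severe grade for a test lies wholly below the SAP's listing cut-off, subjects the protocol would call Grade 3 do not appear in the listing whose title suggests that it contains them. Lymphopenia is the most important case, given the focus in protocol 7.3.3. Grade 3 also carries two meanings in one report: RCTC in the adverse-event tables and CTC in the laboratory listing.

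**Working it through.** **1. Are the SAP's own figures consistent?** Tables 8 and 9 contain 23 cut-offs (18 chemistry, 5 haematology). Each was compared with the point where Grade 3 begins in SAP Appendix 12.8, and 23 of 23 agree. The issue is the choice of scale, not a transcription error.

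**2. How much of each RCTC Grade 3 band does the SAP reach?** Inputs are protocol Appendix 10.3 (rows K2–K5, L10–L14), SAP Tables 8–9 and the liver criteria in SAP 10.3.1. Each RCTC Grade 3 band was stepped through in units of 0.1, so the number of steps is (upper − lower)/0.1 + 1. For creatinine that is (3.0 − 1.9)/0.1 + 1 = 12, and none of the 12 exceeds 3.0. Blood counts are taken as x1000 per microlitre, which equals 10^9/L; this is an assumption, because the RCTC heading prints no volume. Enzymes, bilirubin and creatinine are in multiples of ULN.

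| Test | RCTC Grade 3 | RCTC Grade 4 | SAP Grade ≥3 | Steps in CTC listing | SAP 10.3.1 | Steps in either output |
|---|---|---|---|---|---|---|
| Lymphocytes | 0.5–0.9 | <0.5 | <0.5 | 0/5 | none | **0/5** |
| Creatinine | 1.9–3.0 | >3.0 | >3.0 | 0/12 | none | **0/12** |
| Total bilirubin | 2.0–3.0 | >3.0 | >3.0 | 0/11 | ≥2 | 11/11 |
| ALP | 3.0–5.0 | >5.0 | >5.0 | 0/21 | ≥1.5 | 21/21 |
| AST | 3.1–8.0 | >8.0 | >5.0 | 30/50 | ≥3 | 50/50 |
| ALT | 3.0–8.0 | >8.0 | >5.0 | 30/51 | ≥3 | 51/51 |
| Neutrophils | 0.5–0.9 | <0.5 | <1.0 | 5/5 | none | 5/5 |
| WBC | 1.0–1.9 | <1.0 | <2.0 | 10/10 | none | 10/10 |
| Platelets | 20–49.9 | <20 | <50 | 300/300 | none | 300/300 |

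Under SAP Appendix 12.8, the missed creatinine values are all CTC Grade 2. Lymphocytes of 0.5–0.7 are CTC Grade 2, and 0.8–0.9 are at most Grade 1.

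**3. Haemoglobin.** RCTC row K1 grades the fall from pre-treatment: 2.1–2.9 g/dl is Grade 3 and 3.0 g/dl or more is Grade 4. It also has absolute limits below 8.0 g/dl. SAP Table 9 has only the absolute limit, below 80 g/L. With baseline B and fall F in g/L (g/dl x 10), a subject is unlisted when B − F ≥ 80.

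- The smallest Grade 3 fall goes unlisted from B = 80 + 21 = 101 g/L upward.
- The whole Grade 3 fall band goes unlisted from B = 80 + 29 = 109 g/L upward.
- Grade 4 falls can go unlisted from B = 80 + 30 = 110 g/L upward.

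Take an illustrative baseline of 140 g/L. Falls of 21–29 leave 111–119, and Grade 4 falls of 30–60 leave 80–110; none is listed. A fall from 140 to 105 is 3.5 g/dl, which is RCTC Grade 4 but at most CTC Grade 1.

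**4. Do the other SAP laboratory outputs fill the gap?** The shift tables in SAP 10.3.2 use low/normal/high categories and the last assessment in each period, so a low that recovers is lost and depth is not shown. The change-from-baseline summaries carry no grade. Their minimum would show the largest fall, but not how many subjects had such a fall or who they were. SAP 10.3.1 counts subjects crossing a threshold for liver tests only.

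**The case against.** Five points can be made for the SAP.

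- **The protocol does not require an RCTC laboratory listing.** Protocol 5.2.3 concerns grading values judged clinically relevant, and 7.3.3 names no toxicity scale for the laboratory analysis. The CTC listing is an addition to what 7.3.3 asks for. This stands: the SAP breaks no explicit instruction. The unexplained change of scale and the coverage gap remain.
- **The values can surface elsewhere.** Under protocol 5.2.2.2, laboratory changes judged clinically relevant are recorded as adverse events. SAP 10.2.1.3 grades these by RCTC and describes Grade 3 or higher in detail. Protocol 7.3.3 also has out-of-range and clinically relevant values highlighted in listings. So a reader who inferred that these abnormalities are never reported would be wrong. But the adverse-event route depends on investigator judgement, and highlighting neither grades nor selects. A threshold listing finds values regardless of judgement.
- **Liver tests are covered.** From Tables 8 and 9 alone, one might infer that severe bilirubin, ALP and transaminase values are lost as well. SAP 10.3.1 tabulates and lists them from lower limits, as the table above shows.
- **The effect is not one-way.** It is tempting to say that the switch makes the safety profile look cleaner. For low sodium (<130 against RCTC Grade 3 of 120–124) and high potassium (>6.0 against 6.5–7.0), the SAP is the more sensitive. It also has limits for albumin, triglycerides, cholesterol, GGT and high sodium, for which the RCTC table has no row.
- **Replacing CTC with RCTC would do harm.** It would drop those limits and import bands that overlap as printed: ALP Grade 1 is 1.1–2.0 and Grade 2 is 1.6–3.0, and ALT 3.0 x ULN falls in both Grades 2 and 3. CPK Grade 3 depends on weakness, which a laboratory value cannot show. This stands, and it decides the form of the fix.

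**Conclusion.** The point holds for lymphocytes, creatinine and haemoglobin falls. The SAP's threshold-based laboratory outputs reach none of the RCTC Grade 3 band for lymphocytes (0 of 5 steps) or creatinine (0 of 12). They also miss RCTC Grade 3–4 haemoglobin falls that leave the value at or above 80 g/L. Neutrophils, WBC and platelets agree on the two scales, and the liver tests are covered by SAP 10.3.1.

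The documents support neither a claim of suppressed findings nor one of a consistent bias towards a cleaner profile. The two scales are labelled where they are used, and CTC is stricter for some electrolytes.

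The conclusion rests on the cut-offs as printed and on the unit reading stated above. The number of subjects affected cannot be estimated, because the documents give no distribution of these tests in the roughly 60 planned patients. No test or sample size depends on the point. It is worth correcting because long-term safety is the primary objective and lymphopenia lies within the stated laboratory focus.

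**What to change.** Keep the CTC v4.0 listing in SAP 10.3.2. Extend it to subjects who meet RCTC v2.0 Grade 3 or above for:

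- lymphocytes: 0.9 x10^9/L or lower;
- creatinine: 1.9 x ULN or higher;
- haemoglobin: a fall of 2.1 g/dl or more from pre-treatment, or the RCTC absolute limits.

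Add a column with the grade on each scale, and apply the existing higher-than-baseline condition within each scale. State that pre-treatment means the safety baseline in SAP 6.1. Say how values between printed RCTC bands are handled (for example lymphocytes of 0.95), such as by rounding to one decimal before grading. Add one sentence to the SAP naming the two scales and the reason for using both.

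The data are already collected. The cost is a somewhat longer listing, a little more programming and a short SAP edit.

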10.4 Analysis of Vital Signs

10.4.1 Variables and Criteria Defining Abnormality

Vital sign variables include systolic blood pressure, diastolic blood pressure, pulse rate, body temperature, and weight. The criteria for potentially clinically significant key vital sign findings are presented in [Table 10](#).

Table 10. Criteria for Potentially Clinically Significant Vital Sign Findings

Vital Sign	Category	Criteria for Potential Clinically Significant Vital Signs
Systolic blood pressure (mmHg)	Low	Value \leq 90 mmHg and decrease \geq 20 mmHg from Baseline
	High	Value \geq 160 mmHg and increase \geq 20 mmHg from Baseline
Diastolic blood pressure (mmHg)	Low	Value \leq 50 mmHg and decrease \geq 10 mmHg from Baseline
	High	Value \geq 100 mmHg and increase \geq 10 mmHg from Baseline
Pulse rate (bpm)	Low	Value \leq 50 bpm and decrease \geq 15 bpm from Baseline
	High	Value \geq 120 bpm and increase \geq 15 bpm from Baseline

10.4.2 Statistical Methods

The following summary statistics for all vital sign variables will be presented by treatment group: baseline mean, the mean at each visit, mean change from baseline, standard deviation, median, minimum, and maximum. The number and percentage of subjects meeting the criteria for potentially clinically significant key vital sign values will be summarized.

Vital sign results for subjects with values meeting the criteria for potentially clinically significant vital sign findings will be identified in a listing.

10.5 Analysis of ECG Parameters

ECG abnormalities if assessed by the Investigator as clinically significant will be reported as AE. ECG abnormalities assessed by the Investigator as no clinically significant, will not be captured. Hence no ECG analyses (categorical or outlier) will be performed.

11.0 Summary of Changes

Boehringer Ingelheim Pharma GmbH & Co. KG (BIP) and AbbVie S.A.R.L. (AbbVie) have entered into an agreement whereby AbbVie will take on the responsibilities for the development and commercialization of risankizumab (BI 655066/ABBV-066).

The current SAP has adapted the TSAP initial version developed by Boehringer Ingelheim (BI) which was dated by July 15, 2016. AbbVie analysis conventions are applied.

12.0 Appendix

12.1 Crohn's Disease Activity Index (CDAI)

The Crohn's Disease Activity Index (CDAI) is a composite instrument that includes patient symptoms evaluated over 7 days (abdominal pain, stool frequency and general well-being), as well as physical and laboratory findings. These items are scored individually, weighted, and do not contribute equally to the overall score. The CDAI is derived from summing up the weighted individual scores of eight items as outlined below:

Variable	Description		Weight
Number of liquid stools	Sum of 7 days		2
Abdominal pain	Sum of 7 days ratings	Range: 0 (none) to 3 (severe)	5
General well being	Sum of 7 days ratings	Range: 0 (generally well) to 4 (terrible)	7
Extraintestinal complications	Number of listed complications	arthritis/arthralgia, iritis/uveitis, erythema nodosum, pyoderma gangrenosum, aphthous stomatitis, anal fissure/fistula/abscess, fever > 37.8°C	20
Antidiarrhoeal drugs	Use in previous 7 days	0 (no) or 1 (yes)	30
Abdominal mass		0 (no), 2 (questionable) or 5 (definite)	10
Hematocrit	Expected minus observed hematocrit	Males: 47 minus observed Females: 42 minus observed	6
Body weight [#]	Observed/ideal ratio	[1 – (observed/ideal)] × 100	1

[#] For body weight, if the calculated value is less than –10 then the value is set to –10.

CDAI approximately ranges from 0 to 600 with higher scores indicating more severe disease. For the calculation of CDAI and components at each visit, the following rules will be applied:

- The 7 most recent useable days out of the 14 days preceding the visit will be used.
- If 7 useable days are not available, an average will be calculated based on the number of days with available data as follows:
 - An average for the most recent 6 days will be calculated if data for only 6 days are available,
 - An average for the most recent 5 days will be calculated if data for only 5 days are available,
 - An average for the most recent 4 days will be calculated if data for only 4 days are available,
 - Data for days with missing diary entries will be imputed using the average of the non-missing days, in order to calculate a CDAI and components based on 7 days.
- If the minimum number of days of diary data (i.e., 4 days for CDAI and components) are not available, then the subject's score for that visit will be considered missing and NRI will be used for any endpoints relating to data for this visit.

The CDAI score is set to missing under the following conditions:

1. If there are less than 4 days of any diary data.
2. If any component other than the diary data is missing.

